8.3.2.3 Rate of Severe Infections

Infections will be recorded as adverse events. The infections of interest in this study are severe infections or opportunistic infectious episodes, defined as infections requiring hospitalization or prolonging hospitalization and/or documented infections by opportunistic pathogens (e.g. interstitial pneumonia, intractable diarrhoea).

The number (%) of subjects reporting severe infections or opportunistic infectious episodes along with the number of events reported will be summarized for the OTL-101 treated and

Final Version 4.0 Page 19 of 27

HSCT control groups (data permitting). In addition, the infection rate will be calculated as the number of infections/the total follow-up time. The rate will be calculated both within each treatment group and for each individual subject. The subject infection rate will be summarized by treatment group using descriptive statistics. In addition to the rate for the entire follow-up period, the rate will be calculated for both the first 12 months following transplant and for the remaining study period.

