11.6.2.4.2 Secondary Efficacy Analyses

Main Secondary Endpoint

- Overall survival and event free survival at 24 months
- Use of immunoglobulin replacement therapy.

Additional Secondary Endpoints

The following will be presented for the infection endpoint:

- Frequency table for number and percent of patients who experienced 0, 1, 2, or at least 3 infections,
- Rate of infection will be calculated on the basis of person-years.

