5.2 Secondary Endpoints

Secondary endpoints for this study are:

- Overall survival and event-free survival at 24 months
- Efficacy of gene transfer/engraftment of HSC
- ADA expression: enzyme activity and detoxification

Final Version 4.0 Page 10 of 27

- Effects on ADA reconstitution on immune phenotype and function (the need for IgRT will be assessed under this category)
- Immune reconstitution
- Infection rates

6 Timing of Analyses

The statistical analyses of data from this study will be performed in three stages:

Interim look:

- Performed after all subjects have completed 6 months of follow-up post infusion
- Descriptive statistics for all available data
- Comparisons between OTL-101 treated subjects and HSCT control cohorts of demographics and overall survival

Primary analysis:

- Performed after all subjects have completed 12 months of follow-up post infusion
- Descriptive statistics for all available data
- Comparison to HSCT control cohorts on overall and event-free survival (primary efficacy endpoints), use of immunoglobulin replacement therapy (IgRT) and infection rate (key secondary endpoints).

End of study analysis:

- Performed after all subjects have completed the study (24 months of follow-up post infusion)
- Descriptive statistics for the complete study cohort
- Comparison to HSCT control cohorts on overall and event-free survival (primary efficacy endpoints), use of immunoglobulin replacement therapy (IgRT) and infection rate (key secondary endpoints).

7 Analysis Populations

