7.2 Safety Population

The safety population will consist of all subjects treated with OTL-101 at UCLA/NIH (current study cohort) and the complete HSCT historical control cohort consisting of ADA-SCID patients with any type of donor treated with HSCT at either GOSH or Duke University from the year 2000 onwards.

8 Statistical Methods

In general, continuous variables will be summarised using the mean, standard deviation, median, minimum, maximum and number of subjects. Categorical variables will be summarised using number of subjects and percentages.

For all summaries, the HSCT controls will be summarised in the groups of those without a matched related donor, those with a matched related donor and all subjects.

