8.3 Efficacy Evaluations

The primary comparison for all efficacy analyses will be between the OTL-101 treated subjects and the allogeneic HSCT controls treated at either GOSH or Duke University without a matched related donor.

Secondary comparisons will be between:

- the OTL-101 treated subjects and the HSCT controls treated at either GOSH or Duke University with a matched related donor;
- the OTL-101 treated subjects and the total group of HSCT controls.

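### The key secondary infection comparison has two planned rates, no named main estimate, and no rate ratio, difference or confidence interval; one of its summaries, the mean of subject rates, is easily distorted by early deaths.

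*SAP*

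**What the plan says.** SAP section 6 (Timing of Analyses) lists, for both the primary and the end-of-study analysis, a comparison with the HSCT cohorts on survival and on "use of immunoglobulin replacement therapy (IgRT) and infection rate (key secondary endpoints". SAP 8.3 sets the contrast: "The primary comparison for all efficacy analyses will be between the OTL-101 treated subjects and the allogeneic HSCT controls" without a matched related donor.

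The analysis itself is in SAP 8.3.2.3. It plans the number and percentage of children with a severe or opportunistic infection and the number of events. It then says that "the infection rate will be calculated as the number of infections/the total follow-up time", and that "The rate will be calculated both within each treatment group and for each individual subject". The group-level figure is a pooled person-time rate. For the child-level figures, "The subject infection rate will be summarized by treatment group using descriptive statistics". The opening of SAP section 8 defines such a summary: "continuous variables will be summarised using the mean, standard deviation, median, minimum, maximum and number of subjects". Beyond the whole follow-up, "the rate will be calculated for both the first 12 months following transplant and for the remaining study period".

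Protocol 11.6.2.4.2 mentions only a person-time rate: "Rate of infection will be calculated on the basis of person-years". SAP 8.2.17 reports total subject-years per group.

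Neither document gives a rate ratio, rate difference, confidence interval, model or test for infections, or says which of the two SAP rates is the main estimate.

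**The concern.** A comparison that the SAP itself calls key should yield an estimate of the difference between groups and a statement of its precision. Here it yields two unlinked sets of group figures. Survival, by contrast, gets exact intervals, a difference with a 95% CI, a log-rank test and a Bayesian analysis (SAP 8.3.1.1).

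The only rate summary that carries a measure of spread is the one for subject rates, and its mean is the weakest of the planned statistics. Dividing each child's count by that child's own follow-up and averaging gives two months the same weight as two years. One infection before death at two months enters as 6 per year.

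Short follow-up through death is more plausible among controls. Protocol section 2.1.3.1 cites overall survival of 66% with matched unrelated and 43% with haploidentical donors. Protocol 2.1.6.2 reports 100% survival in 18 evaluable OTL-101 patients at the March 2016 cut-off. If early control deaths tend to follow infections, the mean of subject rates would overstate the control burden, in OTL-101's favour. With neither rate named as main, the choice of which to put forward stays open until the data are seen.

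**Working it through.** The plan gives no expected infection rate or precision for this endpoint, so there is no figure of its own to reproduce. The check compares the planned estimators on assumed data.

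**From the documents.** OTL-101: 20 children followed for 24 months, so 20 × 2 = 40 person-years if complete. Controls: 25 at GOSH and 10 at Duke, any donor type (Protocol Appendix H). The number without a matched related donor is not given.

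**Assumed.** The number of unmatched-donor controls, the number and timing of early deaths, and all infection counts.

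**Formulas.** For child i with x_i infections in t_i years:
- pooled rate = Σx_i / Σt_i
- mean of subject rates = (1/n) Σ(x_i / t_i)
- rate ratio = (x₁/t₁) / (x₀/t₀), with an exact conditional interval: Clopper-Pearson limits p for x₁ out of x₁ + x₀, each converted by p/(1 − p) × t₀/t₁

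**Example 1: 12-month follow-up.** Of 24 controls, 6 die at 2 months after one infection each and 18 survive with 0.5 infections per year.
- Mean of subject rates: (6 × 6 + 18 × 0.5)/24 = 45/24 = 1.88 per year.
- Pooled: (6 + 9)/(6 × 2/12 + 18 × 1) = 15/19 = 0.79 per person-year.
- The mean is 1.875/0.789 = 2.4 times the pooled rate.

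**Example 2: 24-month follow-up.** Of 20 controls, 3 die at 2 months after one infection each and 17 complete 24 months with one infection each. OTL-101 has 10 infections in 40 person-years.
- Mean: (3 × 6 + 17 × 0.5)/20 = 26.5/20 = 1.32. The 3 deaths supply 18/26.5 = 68% of it.
- Pooled: 20/(3 × 2/12 + 17 × 2) = 20/34.5 = 0.58. The deaths supply 3/20 = 15% of the events.
- Median subject rate: 0.50.
- Pooled rate ratio: 0.25/0.580 = 0.43. The exact limits for 10 of 30 are 0.173 and 0.528. Multiplying the odds by 34.5/40 gives 0.18 to 0.97.
- Ratio built on the mean of subject rates: 0.25/1.325 = 0.19.

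**Range.** The same calculation was run over 27 scenarios: 15, 20 or 25 controls; 1, 3 or 5 deaths; death at 1, 2 or 6 months.

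| Quantity | Lowest | Highest |
|---|---|---|
| Mean of subject rates | 0.56 | 4.33 |
| Share of that mean from early deaths | 14% | 92% |
| Pooled control rate | 0.52 | 0.74 |
| Median subject rate | 0.50 | 0.50 |
| Pooled rate ratio | 0.34 | 0.49 |
| Ratio using mean of subject rates | 0.06 | 0.45 |

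The constant median is partly by construction, since every survivor was given the same rate. The exact interval for the pooled rate ratio excludes 1 in 17 scenarios and includes it in 10.

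**No link between infection and death.** Simulating 20,000 groups of 24 controls at 1 infection per year, with 30% dying between 0.5 and 6 months independently of infection, both estimators average 1.00. The standard error is 0.31 for the mean of subject rates and 0.23 for the pooled rate, about 35% larger. In that case the mean is inefficient but not biased.

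**The case against.** A reader might infer that the comparison rests on the unweighted average of subject rates, and so that early-dying controls dominate the whole endpoint. The documents do not support that. SAP 8.3.2.3 also requires the rate within each group, and the protocol's basis is person-years. The descriptive summary includes the median, and the number of children affected and the event counts are reported too. Early deaths can dominate only one of these statistics. This objection stands.

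Several further points can be made:
- The 2.4-fold gap is one assumed scenario. True: death times, infection counts and the number of unmatched controls are not documented, and with no link between infection and death there is no bias.
- Events and subject-years are both planned, so a reader could compute a rate ratio and exact interval. Also true for the whole follow-up. But a ratio worked out afterwards is not prespecified, and the simple exact interval ignores repeat infections in the same child.
- The protocol places infection among its additional secondary endpoints, and control infection data are retrospective and analysed only as data permit. This limits the weight of the endpoint, and an interval cannot cure non-randomised, retrospective control data. It does not remove the gap, since SAP section 6 names infection rate as a key comparison.
- With 20 treated children and perhaps few events, a negative binomial or robust Poisson fit may be unstable. This is fair, and the fix provides a fallback.

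**Conclusion.** The point holds in this form. SAP 8.3.2.3 plans a pooled person-time rate and an unweighted summary of subject rates, names neither as main, and gives no between-group estimate or interval for a comparison that SAP section 6 calls key. That follows from the text and needs no assumption.

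The distortion is confined to the mean of subject rates, and its size is conditional. In the scenarios examined, that mean ran from 0.56 to 4.33 per year, against 0.52 to 0.74 for the pooled rate. These figures assume that each early control death follows one infection, and they illustrate sensitivity; they do not predict the trial's result. The missing interval matters under the same assumptions, because rate ratios between 0.34 and 0.49 had exact intervals on both sides of 1. Those intervals ignore clustering of infections within a child and are probably too narrow. This should be corrected in the SAP, but it does not undermine the primary endpoints.

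**What to change.** Amend SAP 8.3.2.3 as follows:

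1. Name the group-level person-time rate as the main estimate, in line with the protocol.
2. Add the OTL-101/control rate ratio with a 95% CI for the primary contrast (controls without a matched related donor) and for the two secondary control groups. Estimate it from a count model with log follow-up time as offset that allows for within-child clustering: negative binomial, or Poisson with robust variance.
3. If a group has no events or the model does not fit, use the exact conditional Poisson interval and state that it ignores clustering.
4. Report the rates and ratio for months 0–12 and 12–24. The SAP already splits at 12 months, but its remaining period has no stated upper limit for controls transplanted since 2000.
5. Keep subject-level rates as supportive, shown as median and range, or move them to a listing.

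The cost is SAP wording and one model. No new data are needed. The interval will probably be wide, which is information the reader should have.

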8.3.2.4 Immune Reconstitution

Immune reconstitution will be assessed using lymphocyte subsets. Absolute numbers and percentages of CD3+, CD4+, CD8+ CD4+CD45RA+, CD4+CD45RO+ T-lymphocytes, CD19+ B-lymphocytes and CD16+CD56+ NK cells will be measured.

For each of the lymphocyte subsets, the actual value and change from baseline will be summarized by visit for the OTL-101 treated subjects. The median value and range will be plotted over time on a logarithmic scale and individual counts will be plotted along with the age-dependent normal ranges reported in Table 2.

In addition, statistical testing of the change from baseline to 6 and 12 months will be performed. If the difference is normally distributed, a paired t-test will be used. Otherwise, the Wilcoxon signed rank test will be used.

The trend over time will be examined for each count separately, using mixed models for repeated measures (MMRM) with visit and baseline count as fixed effects, and subject as a random effect, utilizing the compound-symmetry covariance structure. If counts are approximately normally distributed they will be analysed on the original scale. If the distribution is found to be skewed to the right and a log transformation can normalize the data, statistical analysis will be performed on log-transformed data. If the data are still not normal, the data will be ranked in ascending order of magnitude and the analysis will be performed on the ranks.

8.3.2.5 T Cell Receptor Excision Circles (TREC) in the PB

TREC levels will be summarised for OTL-101 treated subjects at each visit using descriptive statistics. Plots of the median and range over time on a logarithmic scale will be produced. In addition, individual subject plots of TREC levels over time will be produced.

8.3.2.6 Engraftment

Engraftment of transduced cells will be assessed using vector gene marking in granulocytes and PBMC.

The vector copy numbers in each type of cell will be summarised for OTL-101 treated subjects by visit using descriptive statistics. In addition, for each cell type, plots of the median and

Final Version 4.0 Page 20 of 27

range for copy numbers over time on a logarithmic scale will be produced along with individual subject plots.

8.3.2.7 ADA Expression, Enzyme Activity and Detoxification

RBC ADA activity, AXP, dAXP and %dAXP will be summarized by visit for the OTL-101 treated subjects. The median value and range will be plotted over time on a logarithmic scale as will the values for individual subjects.

In addition, statistical testing of the change in %dAXP from baseline to 6 and 12 months will be performed. If the difference is normally distributed, a paired t-test will be used. Otherwise, the Wilcoxon signed rank test will be used.

If the %dAXP values are approximately normally distributed, the trend over time will be examined using MMRM with visit and baseline count as fixed effects, and subject as a random effect, utilizing the compound-symmetry covariance structure (if it produces an acceptable fit).

8.3.2.8 T Cell Receptor Vβ Panel Results

For each cell type (CD4 and CD8), each of the $V\beta$ results will be summarised for OTL-101 treated subjects at each visit using descriptive statistics. A panel of plots of the median and range over time on a logarithmic scale will also be produced.

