Secondary Efficacy Endpoint 8: Quantitative immunoglobulins by class

Serum immunoglobulin levels (IgG, IgA and IgM) will be determined by routine clinical laboratory assays. Requirement of immune replacement therapy will be assessed

Secondary Efficacy Endpoint 9: Specific Antibody responses

Serum titers of isohemagglutinin antibodies and antibodies to vaccine antigen tetanus toxoid and to polyribosylphosphate {PRP} will be determined by routine clinical laboratory tests if vaccinations have been administered.

Secondary Efficacy End-point 10: T lymphocyte reconstitution

T lymphocyte production and diversity will be analyzed by measuring PBMC TREC by qPCR and vector integration sites by LAM-PCR, and TCR V β family usage by FACS.

Secondary Efficacy End-point 11: Infection rates will be also measured under immune reconstitution as part of the efficacy assessment of a competent immune system

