11.6 Statistical Methods

11.6.1 Overview

As noted in [Section 11.2](#), the statistical analysis of this data will be done in three stages, which are presented below in [Sections 11.6.2](#), [11.6.3](#) and [11.6.4](#). Since all analyses repeat themselves in the different stages, each will be described in detail the first time it appears, which will be referred to in subsequent sections where it is repeated.

The data will be summarized in tables displaying the mean, standard deviation, median, minimum, maximum and number of subjects per group for continuous data (e.g. age, weight) or in tables displaying count and percentage for categorical data (e.g. gender, previous treatment). Data will be presented by visit, if applicable. Data listing by subject will be provided and, where applicable, presented graphically.

Statistical analyses will be performed and data appendices created with SAS® V9.4 or higher.

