A. Immunophenotyping and determination of absolute numbers of subpopulation:

I. T lymphocytes: Cell surface markers CD3, CD4, CD8, . If the T lymphocyte number is >2 S.D. above normal values for age:

a) If there is evidence of T cell lymphocytosis (CD3), then additional immunophenotypic markers may be done to characterize the stage of differentiation, including: CD1, CD2, CD4+/45RA, CD4+/45RO, TCR α/β , TCR γ/δ ,

b) If there is evidence of TCR α/β , T cell lymphocytosis, then staining for TCR V β usage will be performed, using a broad panel of reagents, e.g., IO Test Beta Mark TM(*Beckman Coulter*).

c) If there is evidence of TCR γ/δ T cell lymphocytosis, then TCR γ and TCR δ usage will be analyzed with a broad spectrum panel.

d) If there is an over-represented TCR family, then PCR for respective TCR monoclonality will be performed.

e) TCR spectratyping may also be used to assess/confirm oligo-monoclonality.

II. B lymphocytes: Cell surface markers CD19 and CD20, Ig κ and Ig λ If there is evidence of abnormal distribution of Ig κ or Ig λ expression, then IgM, IgD, IgG, IgA staining may also be performed to determine if a clonal B cell population is present. If the B lymphocyte number is >2 S.D. above normal values for age:

a) If there is evidence of B cell lymphocytosis (CD19 or CD20), then additional immunophenotypic markers may be done to characterize the stage of differentiation, including: CD10, CD27,

¹ These assays are expected to require 2-5 ml of blood, depending on the WBC count

² These assays are expected to require 5-30 ml of blood, depending on the WBC count

- b) Perform PCR or Southern blot for IgH rearrangement to characterize multiple myeloma, macroglobulinemia and lymphoma, for example.
- c) Perform PCR for EBV (to evaluate for Epstein-Barr infection).
- d) BCR spectratyping may also be used to assess/confirm oligo-monoclonality.

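### SAP 8.3.2.8 summarises TCR Vβ usage family by family across children, so the diversity part of secondary endpoint 10 has no analysis at the level of the child

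*SAP*

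**What the plan says.** Protocol 4.2.2, Secondary Efficacy End-point 10, states: "T lymphocyte production and diversity will be analyzed by measuring PBMC TREC by qPCR and vector integration sites by LAM-PCR". It names TCR Vβ family usage by flow cytometry as the third measure.

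SAP 8.3.2.8 takes CD4 and CD8 separately and, for each Vβ, plans that "results will be summarised for OTL-101 treated subjects at each visit using descriptive statistics". It then adds: "A panel of plots of the median and range over time on a logarithmic scale will also be produced". The opening of SAP Section 8 says what descriptive statistics are: "continuous variables will be summarised using the mean, standard deviation, median, minimum, maximum and number of subjects".

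The other two measures in endpoint 10 are treated as follows.

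- **TREC (SAP 8.3.2.5):** summarised by visit, and "individual subject plots of TREC levels over time will be produced".
- **Integration sites:** I found no analysis in the SAP. The nearest section, 8.3.2.6, says "Engraftment of transduced cells will be assessed using vector gene marking in granulocytes and PBMC" and works on vector copy number.

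Protocol 11.6.1 adds a general promise: "Data listing by subject will be provided and, where applicable, presented graphically".

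**The concern.** Diversity is a property of one child's repertoire: how evenly that child's T cells are spread over the families. SAP 8.3.2.8 works in the other direction. It fixes a family and describes it over children, so the link between the families of one child is lost before anything is summarised.

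The SAP does look at the child elsewhere. Lymphocyte subsets, TREC, vector copy number and the ADA measures all get individual plots (8.3.2.4 to 8.3.2.7), and stimulation indices get counts of subjects above and below the normal range (8.3.2.9). Vβ gets neither, although its meaning lies in the pattern within a child.

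At stake is whether the study report can say how many treated children rebuilt a broad repertoire, and whether each child's repertoire widened over follow-up.

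**Working it through.** The documents give no figure for Vβ, so there is none to reproduce. The check asks whether the planned table determines diversity per child.

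**Inputs**
- Children: n = 20 (Protocol 11.4).
- Families: K is not stated. I assume K = 20 and repeat with K = 24.
- Each child's shares sum to 100%, and panels are complete.

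**Formulas**
- Per family, over children: mean, SD (divisor n − 1), median, minimum, maximum.
- Per child, over families: H = −Σ p ln p; effective number of families = exp(H); normalised entropy = H / ln K.

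**Two cohorts, K = 20**
- Cohort A: 10 children have all 20 families at 5%. The other 10 have 10 families at 10% and 10 at 0%, with the missing half alternating between children.
- Cohort B: every child has 10 families at 5%, 5 at 0% and 5 at 10%, rotated over children.

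**The planned table.** In both cohorts every family has 10 children at 5%, 5 at 0% and 5 at 10%. So:
- mean = (10×5 + 5×0 + 5×10)/20 = 5
- SD = √[(5×25 + 5×25)/19] = √13.16 = 3.63
- median 5, minimum 0, maximum 10.

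The tables and plots are identical for all 20 families.

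**Per child**
- A: exp(H) = 20 in ten children and 10 in the other ten.
- B: H = 0.5×ln 20 + 0.5×ln 10 = 2.649, so exp(H) = 14.1 in all twenty.

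With K = 24 the tables again agree (mean 4.17, SD 3.02, median 4.17, range 0 to 8.33). A has 24 and 12 effective families; B has 17.0.

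**Change within a child.** If the even and restricted halves of cohort A exchange places between two visits, every table is unchanged. Yet ten children go from 20 to 10 effective families and ten go from 10 to 20.

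**The plot alone.** Put one family at 50% in m of 20 children, with their other 19 families at 50/19 = 2.63%, and leave all other children even at 5%. For m = 2 and for m = 9 that family shows median 5 and range 5 to 50, and every other family shows median 5 and range 2.63 to 5. The table does differ here: that family's mean is (2×50 + 18×5)/20 = 9.5 against (9×50 + 11×5)/20 = 25.25.

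**What an index per child would show.** Normalised entropy in A is 1.00 in ten children and ln 10/ln 20 = 0.769 in ten; in B it is 2.649/2.996 = 0.884 in all. The means agree (0.884), as do the medians. The cohorts separate on SD (0.119 against 0) and range (0.77 to 1.00 against 0.88 to 0.88). The spread and individual values must therefore be reported, not only the average.

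**The case against.** The case against has real force, and most of it limits the point rather than removing it.

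- **A reader might infer that skewed and even cohorts give similar median plots.** They need not. In simulated cohorts of 20 children with 24 families assumed, where each child has an extra 40% in one randomly chosen family, family medians ran from 2.2% to 2.9%, against 3.6% to 4.6% with even usage. These do not overlap. About 14 of 24 families had a maximum above 30%, and the average family SD was 6.2 against 0.9 percentage points. The planned range and SD would reveal such skew.
- **A reader might infer that endpoint 10 as a whole goes unanswered.** It does not. TREC addresses production and has individual plots. With complete panels, even the cohort-mean Simpson concentration follows from the table as Σ[mean² + (n−1)/n × SD²] = 20 × [0.05² + 0.95 × 0.0363²] = 0.075 in both cohorts. The SAP does not plan that calculation, and it gives no child's value and no spread.
- **A reader might infer that the safety signal of clonal skewing is lost.** It is not. Protocol Appendix F monitors each patient: LAM-PCR when gene-marked cells exceed 1%, then further work-up if monoclonality is suggested. Within that work-up, "If there is an over-represented TCR family, then PCR for respective TCR monoclonality will be performed". Monoclonal expansion in one subject is also a halting criterion (Protocol 9.9).
- **Listings by subject are promised.** With 20 children, a reader could inspect each profile. That stands, but a listing is not a pre-specified analysis.

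This is also one component of one of eleven numbered secondary efficacy endpoints, and it is descriptive. None of these points supplies a diversity measure within a child.

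**Conclusion.** The point holds for the diversity half of endpoint 10. The planned Vβ output can flag that some child has an extreme family. It cannot say how many children have a restricted repertoire, how diversity is spread between children, or how it moves within a child. As the SAP has no integration-site analysis either, no planned analysis covers diversity at that level.

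The size is shown by the two cohorts with identical tables: effective families of 20 and 10 in equal halves, against 14.1 throughout. They are constructed to show what the table leaves undetermined and do not predict what the trial will find. They rest on an assumed number of families and on complete panels; the result is the same at 20 and at 24 families. The primary endpoints are not affected. I would call this a cheap improvement.

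**What to change.** Add to SAP 8.3.2.8:

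1. For each child, visit and cell type (CD4, CD8), compute one pre-specified diversity index, for example normalised Shannon entropy.
2. Summarise it by visit with the full descriptive set, including SD and range, and with change from baseline.
3. Add individual subject plots, as 8.3.2.5 already does for TREC.
4. If the laboratory supplies Vβ reference ranges, add the number of families outside range per child. The documents state no such ranges, so this part is conditional.
5. Keep the panel by family as a supplementary figure.

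No new samples are needed. The schedule has Vβ at baseline and at 6, 12, 18 and 24 months, so at most 20 × 5 × 2 = 200 index values arise. The cost is a few lines of SAP text, a short derivation and one more descriptive table.
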